### **7.4 Additional Outcomes not Specified in Study Research Strategy**

We will also undertake analysis of a variety of other secondary study outcomes including stool microbiome conducted on a subset of study participants.

## **8 Other Data and Definitions**

### **8.1 Demographics and Participant Characteristics**

#### **8.1.1 Race**

All screened subjects will select as many races as applicable. For the analysis, race will be defined as non-Hispanic black, white, or other and analysis by race will compare NHB to other.

| Table 2, Race Categories           |
|---|
| White                                     |
| Black or African-American                 |
| Asian                                     |
| American Indian or Alaska Native          |
| Native Hawaiian or Other Pacific Islander |
| Some other race                           |

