Objectives[*]:	Primary Aim (efficacy): Weight loss at 24 months. Hypothesis: Mean weight loss in the intervention group will exceed that in augmented usual care by $\geq 4\%$ of initial body weight (e.g., $\geq 5\%$ intervention, $\sim 1\%$ control). Secondary weight outcomes: Assess difference between study groups in proportion losing $\geq 5\%$ body weight and differences in mean weight loss and proportion losing $\geq 5\%$ across 3 pre-specified subgroups: 1) with vs. without diabetes; 2) females vs. males; and 3) Whites vs. African Americans. Secondary Aim 1—Physiologic and Lifestyle Outcomes: Assess change in blood pressure, A1c, markers of inflammation, skin carotenoids, and self-reported dietary patterns by study group. Secondary Aim 2—Process and Psychosocial Factors: Assess process variables (attendance, fidelity, and acceptability of the Med-style dietary intervention), and key behavioral and psychosocial variables, including self-regulation/monitoring skills, self-efficacy, motivation, and quality of life. Secondary Aim 3—Economic Outcomes: Assess implementation cost, and incremental cost-effectiveness of the intervention relative to control in terms of cost per percentage reduction in weight (i.e., kg lost) and cost per quality adjusted life years (QALYs) gained. Exploratory Outcome—Stool Microbiome: Assess change in stool microbiome in response to the interventions.
Endpoints[*]:	As outlined above under aims.
Study Population:	Participants will be enrolled in central and eastern North Carolina. The overall sample size is 360. We will conduct contemporaneous enrollment of sub-groups to ensure that at least 40% of participants will be African American, diagnosed with diabetes, and male.
Phase[*] or Stage:	Phase III
Description of Sites/Facilities Enrolling Participants:	Participants will be recruited from the UNC Department of Medicine Internal Medicine Clinic in Chapel Hill, at least 2 community practices within 20 miles of Chapel Hill, and at least 2 community practices from eastern North Carolina.

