4.2 SCIENTIFIC RATIONALE FOR STUDY DESIGN

Rationale for study design and RCT overview: We propose an explanatory RCT to assess the efficacy of our weight loss intervention. As the type of intervention we propose has not been previously studied in a primary care setting (or otherwise) in the US, we believe there is sufficient scientific equipoise to undertake an explanatory trial. The primary focus of the intervention will be on dietary behaviors, though general information on physical activity will also be given (to the extent we anticipate this will be addressed in the augmented control group). Specifically, our focus is to isolate and study the effect of the proposed Med-style dietary pattern on weight loss. We propose a sample larger than needed to test

the primary outcome as it allows us to address secondary weight loss outcomes in 3 pre-specified subgroups: 1) those diagnosed with vs. without type 2 diabetes (hereafter, we will use “diabetes” to indicate “type 2 diabetes”), 2) female vs. male, and 3) whites vs. African Americans. All of these subgroups will comprise at least 40% of the study sample. As we are proposing a behavioral intervention trial with the methodological challenges of a non-blinded RCT,⁷⁶ we will adhere to the updated (2017) recommendations outlined in the CONSORT statement for randomized trials of non-pharmacologic treatments.⁷⁶

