Selecting participants to assess interest and confirm eligibility: Our goal is to enroll at least 40% of participants with diabetes, African American, and males and our plan is to enroll and achieve this ratio contemporaneously, through a series of cycles as outlined below. Our enrollment dataset will include participants' screening ID, diabetes status, sex, and race (from the EHR – we will ask participants to report race on our demographic form and this will be the official race variable). We anticipate that most of the potential participants will have been referred to the study by their PCP before we commence selecting participants for a Wave. However, if PCPs who are tardy in referring potential participants to the study do so after a cycle, their patients will be added to the pool for the next cycle.

We will invite participants to participate in sequential “cycles” separated by approximately 1 month. We anticipate about 1/4 of those invited will participate and our hope is to complete enrollment in four sequential cycles, so we will start with a cycle size of 120 for the UNC site (enrollment goal = 120) and 60 participants for each of the four community practices (enrollment goal per practice = 60). (If it turns out our recruitment strategy at community practices focuses more on clinicians than practices, as in 8 clinicians from 4 practices, we will adjust our numbers accordingly. We will consider this condition to

represent a virtual practice and will follow this protocol for contemporaneous enrollment of sub-groups as if it was one practice.) There are eight possible combinations from crossing the three sub-groups of interest (Table 1 below). In the first cycle at the UNC site, the list will include 120 potential participants with 12-18 potential participants per subgroup. To align with the pool of applicants, we will initially invite a minimum of 40% from each subgroups. We will select 1) 4 subgroups with the fewest participants in each cell or 2) (if subgroups are similar in size), the 4 subgroups with low Ns that includes those anticipated to be most difficult to recruit (e.g. males) for 40% enrollment. This approach should allow us to achieve a minimum of 40% in each subgroup.

Table 1. Number of potential participants per sub-group for the first cycle of screening

Subgroup	Participant with Diabetes	African American	Female	UNC		Other practices	
				N	%	N	%
1	Yes	Yes	Yes	18	0.15	9	0.15
2	Yes	Yes	No	12	0.10	6	0.10
3	Yes	No	Yes	18	0.15	9	0.15

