9 STATISTICAL CONSIDERATIONS

9.1 STATISTICAL HYPOTHESES

This randomized trial will compare the effects of a Mediterranean-style (Med-style) dietary pattern intervention to an augmented usual care control group in primary care clinics. The objectives of this trial are:

Primary Aim (efficacy): Weight loss at 24 months. Hypothesis: Mean weight loss in the intervention group will exceed that in augmented usual care by $\geq 4\%$ of initial body weight (e.g., $\geq 5\%$ intervention, $\sim 1\%$ control).

Secondary weight outcomes: Assess difference between study groups in proportion losing $\geq 5\%$ body weight and differences in mean weight loss and proportion losing $\geq 5\%$ across 3 pre-specified subgroups: 1) with vs. without diabetes; 2) females vs. males; and 3) Whites vs. African Americans.

Secondary Aim 1—Physiologic and Lifestyle Outcomes: Assess change in blood pressure, A1c, markers of inflammation, skin carotenoids, and self-reported dietary patterns by study group.

Secondary Aim 2—Process and Psychosocial Factors: Assess process variables (attendance, fidelity, and acceptability of the Med-style dietary intervention), and key behavioral and psychosocial variables, including self-regulation/monitoring skills, self-efficacy, motivation, and quality of life.

Secondary Aim 3--Economic Outcomes: Assess implementation cost, and incremental cost-effectiveness of the intervention relative to control in terms of cost per percentage reduction in weight (i.e., kg lost) and cost per quality adjusted life years (QALYs) gained.

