### 9.4.1

### Primary Efficacy Analyses

The primary analyses will be conducted using the ITT Population (i.e., all randomized participants) and will be repeated secondarily using the Per Protocol Population. We will compare the longitudinal mean % change in body weight between groups using analysis of covariance (ANCOVA), conducted using a linear mixed model. A mixed model will allow for the inclusion of all observed follow-up data for all participants. The model will include fixed effects for group, follow-up visit (4, 12, or 24 months), group-by-visit interactions, site (see operational definition as below), baseline weight, race/ethnicity, gender, and diabetes status. (When reviewing the analysis in May, 2025, we realize we inadvertently did not include age in the model. Our final models included age.) There is no plan to include other baseline variables (including those different) in the model. To account for within-participant correlation, the model will allow for correlated error terms using an unstructured covariance matrix. For the primary comparison, we will use a linear contrast (i.e., group -1 1 group\*follow-up visit 0 0 -1 0 0 1) of the model parameters to test for a treatment effect at 24-months at the 5% significance level. Secondarily, we will compare the groups at other time points and will estimate effect sizes along with 95% confidence intervals for each comparison. Additionally, we will expand the model by including appropriate interaction terms, one at a time, to examine the potential heterogeneity of intervention effect in sub-groups, including diagnosis (diabetes vs. no diabetes), race/ethnicity, sex (for gender, 2 participants not binary, so will for these will use sex as captured in the electronic health record), and by degree of baseline obesity ( $BMI \geq \text{median}$  vs. less). Interaction terms will be tested at the 5% significance level.

Next, we will use a longitudinal mixed effects logistic regression model to compare the groups for proportions losing  $\geq 5\%$  baseline body weight at each follow-up visit. Estimates of odds ratios and 95% confidence intervals will be provided. This model will control for the same covariates specified for the primary model and test the same interaction terms.

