## **9.6 Sample Size Justification**

For our primary outcome, percent change in weight at 24 months, we have calculated sample size based on a two-sided test of significance with  $\alpha=0.05$  and the standard deviation (SD) of percent change in weight of 7.3% as observed in the Heart Health Lenoir Project. Table 5 illustrates sample size calculations (allowing for 20% attrition) for various differences in mean changes between study groups based on a 1:1 randomization allocation ratio. This table also provides power calculations to detect differences in weight change compared to augmented usual care separately for pre-specified subgroups (those with vs. without diabetes, female vs. male, and white vs. African American assuming no sub-group is less than 40% of the overall sample). We expect the intervention to reduce weight by at least 5% and that average weight loss in the intervention group will exceed that in augmented usual care by at least 4% (we estimate weight loss in usual care of  $\leq 1\%$ ). Our plan to enroll 360 participants provides excellent power for our primary outcome

(>99%) and reasonable power (82%) within each of our pre-specified sub-groups. For a difference between groups as small as 3%, we still have robust power for our primary outcome. Although we do not anticipate major differences in weight loss between those in our pre-specified subgroups, we will test the potential for large differential effects between subgroups using interaction terms. However, under the assumptions described above, our power to detect realistic difference in effects of 2-3% between these subgroups will be limited (about 20-40%). Also, for a difference in proportions of those losing  $\geq$  5% body weight as small as 15% (e.g., 15% control vs. 30% intervention), allowing for attrition, the proposed sample size provides 85% power. For several secondary outcomes, we present in Table 5 minimally detectable differences corresponding to effect size of 0.33 for the sample size of 360 with 20% attrition, 80% power, and  $\alpha = 0.05$ .

Note, the table below assume sample size of 350. After funding, the investigative team elected to increase sample size to 360 with a goal of 120 participants per wave.

| Table 5. Power Estimates for % Change in Weight at 24 Month Follow-up |                   |                                    |   |
|--|-------------------|------------------------------------|---|

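### SAP 8.1.1 compares non-Hispanic Black participants with 'other', not the pre-specified Whites versus African Americans; the effect is probably small, but one contrast must be named

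*SAP*

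**What the plan says.** **The objective.** The Protocol synopsis lists the second and third pre-specified subgroup comparisons as "2) females vs. males; and 3) Whites vs. African Americans". Protocol 3 repeats this, Protocol 4.2 has "3) whites vs. African Americans" and Protocol 9.1 has "3) Whites vs. African Americans". SAP objective (b) names the same comparison, for mean weight loss and for the proportion losing at least 5%. SAP 9.6 attaches its subgroup power to "female vs. male, and white vs. African American assuming no sub-group is less than 40% of the overall sample".

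**The operational rule.** SAP 8.1.1 lets participants tick more than one race and then says that "race will be defined as non-Hispanic black, white, or other and analysis by race will compare NHB to other". No other text in either document defines race for the analysis.

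**The model.** SAP 9.4.1 lists the interactions as "including diagnosis (diabetes vs. no diabetes), race/ethnicity, sex" and adds baseline obesity. The logistic model for 5% loss tests the same interactions. Protocol 9.4.2 also says only race/ethnicity, and Protocol 9.4.7 only race. Neither document explains the difference or says which text governs.

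**The concern.** An analyst who codes race exactly as SAP 8.1.1 directs does not produce the comparison that objective (b) promises, either for mean weight change or for 5% loss. The conflict lies inside the SAP as well as between the SAP and the protocol.

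The rule is also ambiguous. It names three levels and then uses the name of the third as the comparator. It gives no place to multi-race participants who report Black. Hispanic Black participants fall outside the first category, although the objective says African American.

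Timing adds to this. SAP 9.4.1 records "When reviewing the analysis in May, 2025, we realize we inadvertently did not include age in the model", so models had been examined by then. With two race contrasts on paper, either could be presented as the planned one unless the SAP says which it is.

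**Working it through.** **Inputs from the documents.** SD 7.3, two-sided 5%, 1:1 allocation, 20% attrition, 4-point effect, subgroups of at least 40% (SAP 9.6); N = 360 (SAP 5.2), with the power table built on 350. Wave size 120; Wave 1 was 55% African American as of 2/22/21 (Protocol 5.5).

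**Assumptions.** Final race counts are not given. I take African American as NHB for the arithmetic, a third category (neither NHB nor White) of 5-15% of the sample, and 360 × 0.8 = 288 analysed.

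**1. The plan's own figures.**
- Within-subgroup: 350 × 0.8 × 0.4 / 2 = 56 per arm. A t test for 4 points with SD 7.3 has 82.0% power, as stated. With N = 360 it is 57.6 per arm and 83.0%.
- Interaction: SE = 7.3 × √(4/n₁ + 4/n₂), where n₁ and n₂ are the race-group totals over both arms. With N = 350 and a 40/60 split (112 and 168), power is 20.2% for 2 points and 39.2% for 3, matching the stated 20-40%.

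**2. Which reading of 8.1.1 is likely.** Protocol 5.5 says "There are eight possible combinations from crossing the three sub-groups of interest", and race enters that grid as African American yes or no. The later enrolment note in the same section calls one non-African American cell white. Both point to NHB versus everyone else.

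**3. Size under the likely reading.** If Waves 2-3 reach 40%, the African American share is (120 × 0.55 + 240 × 0.40)/360 = 45%.
- Groups: 129.6 and 158.4, so SE = 1.729; power 21.2% for 2 points and 41.1% for 3.
- Part of the comparator that is not White: 5/55 = 9.1% to 15/55 = 27.3%.
- Shift in the interaction = that fraction × (effect in the third category minus effect in Whites):

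| Difference in effect | Shift (points) | Shift (SE) |
|---|---|---|
| 1 point | 0.09-0.27 | 0.05-0.16 |
| 2 points | 0.18-0.55 | 0.11-0.32 |
| 4 points | 0.36-1.09 | 0.21-0.63 |

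- Adverse case: if the third category responds like NHB participants, the contrast shrinks by its share of the comparator. For NHB shares of 40-55% that is 8-11% at a 5% third category, 17-22% at 10% and 25-33% at 15%. At 15%, power for 3 points falls to 21-25%.

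**4. Within-group power for 4 points against the African American share (N = 360, t test).**

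| Waves 2-3 average | Overall share | Per arm | Power |
|---|---|---|---|
| 40% | 45% | 64.8 | 87.2% |
| 30% | (66 + 72)/360 = 38.3% | 55.2 | 81.4% |
| 25% | (66 + 60)/360 = 35% | 50.4 | 77.8% |

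The lower rows are plausible: Protocol 5.5 set a 30% target at one Wave 2 practice, where 11% of referrals were Black, and reports smaller African American percentages in Wave 2. The pooled non-NHB group, at 55%, has 79.2 per arm and 92.9%.

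**5. The literal reading (NHB versus the third category only).** 288 × 0.05/2 = 7.2 to 288 × 0.15/2 = 21.6 per arm in that category; within-group power for 4 points is 16-42%.

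**6. African American versus White.** At 45/50, SE = 1.768 and power is 20.5% for 2 points and 39.6% for 3. At 45/40, SE = 1.870 and power is 18.8% and 36.1%. At 40/40, SE = 1.924 and power is 18.0% and 34.5%.

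**The case against.** The strongest reply is that little has changed. Recruitment was built on African American yes or no, the enrolment minimum is set for African Americans, and the enrolment note uses white where the grid says non-African American. If the authors use White as shorthand, the two contrasts are nearly the same split. Whites versus African Americans appears in the objectives and the power text, never in a model specification, so 8.1.1 is the first operational definition and does not reverse an earlier analysis rule. Pooling also keeps every randomised participant in the contrast, which is a legitimate reason to choose it.

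Most of this stands, and it is why the effect is probably small. It does not remove the mismatch: 8.1.1 itself lists white and other as separate levels, so White is not shorthand there, and a sampling grid does not replace a stated objective. If pooling was intended, the SAP should say so and why.

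A reader might infer a results-driven switch. The documents do not support that. The SAP draft is dated 9/10/24, before outcome analysis, 8.1.1 carries no later date, and the May 2025 remark concerns age. A reader might also infer that Whites are left out of the race analysis. The wording permits it, but the enrolment grid makes it the less likely meaning.

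**Conclusion.** The contradiction is real and sits in current text. As written, SAP 8.1.1 does not deliver the race comparison named in SAP objective (b) and the protocol. This is an inconsistency in one secondary, low-powered subgroup analysis. It is not a lost objective, because the three-level race variable still allows a comparison with Whites. The primary contrast is essentially unaffected, since race is only a covariate there.

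Under the likely reading the shift is probably small: 0.11-0.32 SE for a 2-point difference in effect, given a 45% NHB share and a 5-15% third category. The documents cannot prove this. The third-category range is an assumption, and a 10-15% category that responds like NHB participants would dilute the contrast by 17-33%.

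The 82% within-subgroup power should be neither taken as secured nor declared lost: it holds at a 45% African American share and slips to 81% at 38% and 78% at 35%. Confidence is high in the textual mismatch and lower in its size.

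**What to change.** In SAP 8.1.1 and 9.4.1:

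- Name African American versus White as the pre-specified race contrast, for mean weight change and for the proportion losing at least 5%. Estimate it from a three-level group-by-race interaction so that all participants stay in the model.
- Make the first category match that name. State whether Hispanic Black participants and multi-race participants who report Black count as African American. If the category stays NHB, say openly that the contrast is NHB versus White.
- Define 'other'.
- Report NHB versus all others alongside, labelled as the 8.1.1 definition and with its reason.
- Date the correction, and state that it was made after models were reviewed in May 2025 and that it restores the protocol's comparison.

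The cost is a few SAP sentences, one contrast statement and a dated note, with no new data. It adds one unadjusted secondary test. Interaction power is slightly lower than for the pooled split: about 36-40% against 41% for 3 points at a 45% African American share, and 34% if both groups are only 40% of the sample.

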#### **8.1.2 Ethnicity**

All screened subjects will be given the option to report Hispanic or non-Hispanic ethnicity.

#### **8.1.3 Gender**

All screened subjects will be given the option to report gender. For the analysis based on gender, we will include those identified as male and female (note 1 participant identified as trans and 1 non-binary)

| Table 3, Gender |
|------------------------|
| male                   |
| female                 |
| transgender            |
| additional category    |
| non-binary             |

#### 8.1.4

#### Diabetes

A participant will be classified as having diabetes if either 1) a doctor ever told him/her that he/she have diabetes, 2) A1c  $\geq 6.5$ , or 3) are currently using any diabetes medication (Insulin, metformin, sulfonylurea, GLP-1 receptor agonists, SGLT2 inhibitors, thiazolidinediones, and/or DPP-4 inhibitor).

## 9

## Statistical Analysis

### 9.1

### General Considerations

### 9.2

### Data Handling

The primary data collection and management program will be REDCap as administered by the NC TraCS. The data manager and [name] will be responsible for making corrections. A log of all corrections/edits will be maintained.

**Table 4, Data Handling**

| Type/Use of Data   | Data Source   | Data Storage   | Ident. | Data Review/Other Comments  |
|--|---|--|--------|---|
| Data from the electronic medical record                                | NC TraCS data warehouse                                 | 

• NC TraCS server

• HPDP server

        | yes    | These data, extracted from the data warehouse utilized by NC TraCS, will be provided in an Excel format for each primary care clinician at participating study sites. Output will be carefully inspected by research staff for completeness before it is sent to providers who must recommend participation of their patients in this study.  |
| Data for providers to review regarding participation of their patients | Primary care clinicians                                 | HPDP server  | yes    | Providers will either be sent a link to a password protected Excel file with a listing of their patients who meet basic study inclusion criteria or these data will be provided on a password protected thumbdrive (a flash drive or USB stick). They will be asked to review and note the patients who they refer to the study to receive an intensive multimodal weight loss program. |
| Eligibility data   | From participants, collected by phone by research staff | REDCap server  | yes    | Reviewed by staff before randomization.   |
| Consent forms  | Participants  | 

• For consent completed on-line, REDCap server

 | yes    | Research staff insure that consent documents are signed after all questions are answered.   |
| Participant study data collected using REDCap forms and surveys—       | Participants  | REDCap server  | yes    | Surveys and forms will have study ID. Data will be collected via phone for those who do not want to complete online.  |

|   |              |   |            |  |
|---|--------------|---|------------|--|
| electronic questionnaires   |              |   |            |  |
| Willett Food Frequency Questionnaire                                    | Participants | 
 
• Data collected using REDcap version
 
• At Harvard School of Public Health
 
 | no         | Data sent to Harvard is de-identified.   |
| Anthropometrics, blood pressure, skin carotenoids                       | Participants | REDCap server   | yes        | 
Data entered by research field staff from instruments used for these assessments. Note special protocol for primary outcome variable, body weight.
 
 
• For assessment at data collection time points, weight is assessed 2 times. If difference between weights is 1 pound or greater a third assessment is performed. For analysis, weights are averaged, using the 2 weights that differ by less than a pound.
 
• For follow-up assessments, a photo of the weights will be taken and the data entered by study staff blinded to the randomization assignment of participant.
 
 |
| “Clinical” blood work   | Participants | 
 
• At LabCorp per storage of routine lab work.
 
• REDCap
 
                     | yes        | These clinical lab results will be scanned in the electronic health record and except for CRP, results will be reported to participants.   |
| Blood markers of inflammation and diabetes markers (leptin and insulin) | Participants | 
 
• At [name] lab
 
• HPDP
 
   | yes        | Samples will be stored at [name] Lab until all are collected. Results will be entered into Excel spreadsheet and sent to HPDP.   |
| DNA analysis  | Participants | --  | yes        | Blood for DNA analysis will be stored as part of this study for possible future analysis. Samples will be stored at [name] Lab.  |
| Process data collected use Web-based counseling program.                | Participants | 
 
• Sheps server
 
• HPDP
 
  | yes        | Data collected by web-based counseling program. These data will reside on the Sheps Center server until downloaded into a Excel file and sent to HPDP.   |
| Data sets for analysis  | Participants | 
 
• REDCap
 
• HPDP
 
  | yes and no | Analysis datasets created from REDCap datasets. Will be stored on Study's Microsoft Teams account and on the HPDP O drive . These datasets will have identifiers in REDCap. Data exported from REDCap to be used for analysis is de-identified.  |

